### *ACR components - HAQ-DI*

The highest score for any component question in a category determines the category score. If the patient is using assistance for any of these activities, scoring may be adjusted. The total score is the sum of all category scores divided by the number of answered categories. At least 6 categories should be answered in order to have a total score.

### *DAS28-CRP*

When calculating DAS28-CRP, the following rules will be applied in order:

- When calculating the 28TJC and 28SJC, with individual missing joint scores (the “replaced or fused” joints are not taken into consideration for the swelling or tenderness) imputed as the mean of the scored joints, the tender/swollen joint counts after imputation are as follows:

$$28TJC/28SJC = \text{sum (scored tender/swollen joints)} * (\text{number of joints in the full joint set} / \text{number of scored tender/swollen joints})$$

The number of joints in the full joint set is defined as (28 – number of replaced or fused joints) and the scored joints refer to those with an answer (0 – no pain, 1- pain).

- No imputation will be performed.
- If any of the 4 variables: 28TJC, 28SJC, GH (patient global), CRP is missing, then DAS28-CRP will be set to missing.

### ***SF-36***

The score of each of the 36 items is collected on the CRF. [Appendix I](#) provides the SAS code to calculate the 8 scales, the 2 summary measure scores and standardized summary scores.

The PCS and MCS summary measure scores will be computed if at least 50% of the component scales are available. The scale scores will be computed if at least 50% of the items are available and valid within the corresponding scale. The missing items will be imputed by the mean of available items.

### **2.5.3 Missing data**

For categorical variables, patients with missing data are not included in calculations of percentages unless otherwise specified. When relevant, the number of patients with missing data is presented.

#### ***Handling of computation of treatment duration if investigational drug end of treatment date is missing***

For the calculation of the treatment duration, the date of the last dose of IMP is equal to the date of last administration reported on the dosing CRF page. If this date is missing, the exposure duration should be kept as missing.

#### ***Handling of medication missing/partial dates***

No imputation of medication start/end dates or times will be performed. If a medication date or time is missing or partially missing, so it cannot be determined whether it was taken prior or concomitantly, it will be considered as a prior and concomitant medication.

#### ***Handling of AEs with missing or partial date/time of onset***

Missing or partial missing AE onset dates and times will be imputed so that if the partial AE onset date/time information does not indicate that the AE started prior to treatment or after the TEAE period, the AE will be classified as treatment-emergent. No imputation of AE end dates/times will be performed. These data imputations are for categorization purpose only and will not be used in listings. No imputation is planned for date/time of AE resolution.

### ***Handling of AE when date and time of first investigational drug date is missing***

When the date and time of the first investigational drug is missing all adverse events that occurred after or on the day of enrolled should be considered as treatment-emergent adverse events. The exposure duration should be kept as missing.

### ***Handling of missing relationship to investigational product of AEs***

If the assessment of the relationship to investigational product is missing, then the relationship to investigational product has to be assumed and the AE considered as such in the frequency tables of possibly related AEs, but no imputation should be done at the data level.

### ***Handling of missing severity of AEs***

If the severity is missing for one of the treatment-emergent occurrences of an AE, the maximal severity on the remaining occurrences will be considered. If the severity is missing for all the occurrences a “missing” category will be added in summary table.

### ***Handling of PCSA***

If a patient has a missing baseline, that patient will be grouped in the category “normal /missing at baseline”.

For PCSA with two conditions, one based on a change from baseline value or a normal range and the other one on a threshold value, the first condition being missing, the PCSA will be based only on the second condition.

For PCSA defined on a threshold and/or a normal range, this PCSA will be derived using this threshold if the normal range are missing; e.g., for eosinophils the PCSA is  $> 0.5$  Giga/L or  $>ULN$  if  $ULN \geq 0.5$  Giga/L. When ULN is missing the value 0.5 should be used.

Measurements flagged as invalid by the laboratory will not be summarized nor be taken into account in the computation of PCSA values.

## **2.5.4 Windows for time points**

For efficacy parameters (except X-ray), a discontinuation visit (EOT, Visit 49) will be mapped to the scheduled visit for the analyses. If a discontinuation visit happens at a regular visit, then the visit number will be reassigned as the regular visit number where an assessment is planned. If a discontinuation visit happens between 2 regular visits, then the visit number will be reassigned to the next visit number where an assessment is planned. For example, if a discontinuation visit happens between Visits 9 and 10, then the visit number will be reassigned as 10. Similarly, the EOT visit (Visit 49) for patients who complete the study with 260-week treatment duration per Protocol Amendment 8, will be mapped to the Visit 28.

For X-ray data, the linear extrapolation method for the modified total Sharp score, the erosion score, and the joint space narrowing score will use true date to extrapolate missing values at Weeks 48, 96, 144, and 192 with no visit remapping.

All efficacy analyses will be performed by the nominal visit number and no visit window will be defined.

For safety assessments, the reference date for the derivation of relative days of events or findings will be the date of first drug intake as documented in the study drug administration page of the eCRF. Selected safety variables will be summarized using the visit window defined in [Table 6](#) for the by-visit descriptive analysis. Note that only the laboratory measurements performed at the central laboratory will be used for the by-visit descriptive analysis. All available values obtained between two visits including unscheduled measurements will be assigned to the appropriate visit window. The following rule will be applied when mapping the measurements to the visit:

1. When a patient has more than one measurement on the same laboratory parameter (or vital sign or ECG) on the same date, then the one with the later/largest sample ID will be used.
2. For the same laboratory parameter (vital sign or ECG), if a patient has more than one measurement at different dates within the same visit window, the scheduled measurement that is closest to the target date will be used. If there is no scheduled measurement within the visit window, the unscheduled measurement that is closest to the target date will be used.
3. When a patient has more than one measurement on the same laboratory parameter with the same distance from the target date, select the one with the latest date.

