### 11.1 TEMPORARY TREATMENT DISCONTINUATION WITH INVESTIGATIONAL PRODUCT(S)

Temporary treatment discontinuation may be considered by the Investigator because of suspected AEs eg, suspected malignancy or because of abnormal laboratory values.

The following is a list of criteria for temporary discontinuation. This list is not exhaustive and IMP may be temporarily discontinued for additional reasons based on Investigator judgment:

- Increase in ALT level  $\geq 3$  x ULN to  $\leq 5$  x ULN and bilirubin  $\leq 2$  x ULN (unless the patient has documented Gilbert's disease). The IMP can be resumed at the dose of 150 mg q2w only after the ALT has returned to a value  $< 3$  ULN and all requirements for resumption of study drug administration are met (see [Section 10.2.4](#) and [Appendix L](#)).
- Decrease in neutrophil count to a level between 500/mm^3 to  $< 1000$ /mm^3 without signs and symptoms of a potential infection. The IMP can be resumed at the dose of 150 mg q2w only after the neutrophils have returned to a value  $\geq 1000$ /mm^3 and all requirements for resumption of study drug administration are met (see [Section 10.2.5](#) and [Appendix L](#)).
- Decrease in platelet count to between 50 000 cells/mm^3 to  $< 100$  000 cells/mm^3 without spontaneous bleeding. The IMP can be resumed at the dose of 150 mg q2w only after the platelet count is  $\geq 100$  000/mm^3 and all requirements for resumption of study drug administration are met (See [Section 10.2.6](#) and [Appendix L](#)).
- Infections requiring oral or parenteral treatment with antibacterial, antiviral and/or antifungal agents (See [Section 10.2.1](#) for additional guidance)
- Surgery requiring temporary treatment discontinuation of biologic DMARD as per applicable guidelines

If the dose is reduced to 150 mg q2w the reduced dose will be maintained for the whole duration of the treatment period.

The IMP can be temporarily discontinued for  $\leq 59$  days (3 IMP doses can be missed).

Reinitiation of treatment with the IMP will be done under close and appropriate clinical/and or laboratory monitoring.

If the restart of the IMP occurs later than 38 days since the last IMP dose (2 IMP doses were already missed), the IMP has to be administered at the study site and the patient to be observed for 30 minutes for any medical events.

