#### ***Observation period***

The observation period will be divided into 4 epochs:

- The SCREENING epoch is defined as beginning with the last visit in the previous studies to the first dose of IMP in LTS11210
- The TREATMENT epoch is defined as the time from first dose of IMP in LTS11210 to last dose of IMP + 13 days (6 days for patients receiving weekly injections only)
- The FOLLOW-UP epoch is defined as the time from the end of TREATMENT epoch to last dose of IMP + 60 days
- The POST-STUDY epoch is defined as the time after the last dose of IMP + 60 days

The rationale of having “last dose of IMP + 60 days” as the end of follow-up epoch is to capture the events observed within an approximately 5 half-lives of the last IMP. The treatment-emergent AE (TEAE) period will include both TREATMENT and FOLLOW-UP epochs.

Please note: Not all the patients will have all 4 epochs. For example, if a patient died on the 7th day after the last dose of IMP, his/her TREATMENT epoch will be from the first dose of IMP to his/her death date and will have no FOLLOW-UP or POST-STUDY epoch; if a patient had his last visit (i.e. follow-up visit 29) on the 50th day after the last dose of IMP and have no AE reported after this date, his/her FOLLOW-UP epoch will be ended on last dose of IMP+50 days and will have no POST-STUDY epoch.

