### **2.1.5 Pharmacokinetic and immunogenicity variables**

Immunogenicity (anti-sarilumab antibody) and pharmacokinetic blood samples (trough concentrations) will be collected according to the study flow chart. Pharmacokinetic samples will also be collected at or near the onset and completion of the occurrence of a serious adverse event. Note that there are some missing data after Week 48 since pharmacokinetic evaluation were added after Week 48 per Protocol Amendment 8 and by that time some patients already reach more than 48 weeks of treatment.

At each sample time the result of the ADA assay will be categorized as either positive or negative, and in the case of a positive result will be further characterized as either neutralizing or non-neutralizing.

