##### ***Pharmacokinetic variables***

All the PK analyses will be performed using the PK population.

Serum samples will be analyzed for functional SAR153191 concentrations using validated enzyme-linked immunosorbent assay (ELISA) methods with a targeted lower limit of quantitation (LLQ) of 0.294 mg/L (*REGN88-AV-07026-SA-01V1*) or 0.3125 mg/L (*REGN88-AV-13131-VA-01V1*). Serum concentrations of functional sarilumab will be summarized using arithmetic and geometric means, standard deviation (SD), standard error of the mean (SEM), coefficient of variation (CV%), minimum, median and maximum by actual dose and visit. Concentrations below LLOQ were replaced by LLOQ/2.

After the completion of EFC11072 (Mobility) Part B study, the Sponsor made the decision to discontinue measurement of bound sarilumab concentration from ongoing studies globally. Serum concentrations of bound sarilumab (serum sarilumab-sIL-6R $\alpha$  complex) will not be summarized in this study.

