For PK, ADA and Vital signs, the follow-up (ie, 6-week post-treatment) measurement will be defined based on the sample collected at the follow-up Visit 50.

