## Disposition of patients

Below describes patient disposition for both patient study status and the patient analysis populations for the sub-study only, unless otherwise specified.

- All screened patients are defined as those patients who signed the informed consent for the sub-study.
- All enrolled patients are defined as all patients with signed informed consent who met the eligibility criteria to enter into the sub-study.
- The Safety population consists of all enrolled patients who received at least one dose of the IMP administered via PFS-S during this sub-study.
- The PK population consists of all enrolled patients on stable dose of sarilumab (receiving the same dose of sarilumab without treatment interruption) at least 24 weeks prior to V101 until V102 who receive at least 1 dose of the IMP and at least one non-missing serum concentration value during this sub-study.

For patient study status, the total number of patients for each one of the following categories will be presented using a summary table:

- All screened patients (informed consent signed)
- Screen failure patients and reasons for screen failure (not eligible per eligible CRF page)
- Non-enrolled but treated patients
- Enrolled but not treated patients
- Enrolled and treated patients
  - Patients who had stable dose at least 24 weeks prior V101
- Patients who had dose reductions during the duration of the sub-study
- Patients who discontinued the sub-study treatment by main reason for discontinuation
  - Patients who discontinued the sub-study treatment but continues in the main study
  - Patients who permanently discontinued the study treatment during participation in the sub-study
- Status for returning to the main study (Yes/No)

For all categories of patients (except for the screened and non-enrolled categories), percentages will be calculated using the total of all enrolled patients as the denominator. Reasons and time to treatment discontinuation will be supplied in tables giving numbers and percentages.

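### The by-visit sarilumab trough tables place samples by study day with no check on time since the last injection, so off-drug end-of-treatment and interruption samples can be reported as on-treatment troughs

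*SAP*

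**What the plan says.** - **What is summarised.** SAP 2.1.5 states that "pharmacokinetic blood samples (trough concentrations) will be collected according to the study flow chart", and adds samples near the onset and completion of an SAE. SAP 2.4.6 summarises functional sarilumab by arithmetic and geometric mean, "minimum, median and maximum by actual dose and visit". SAP 2.4.8 (ADA and PK) repeats this by ADA status within each actual dose.
- **Who qualifies.** The PK population (SAP 2.3.3) needs only one post-dose value.
- **How a sample gets its visit.** Table 6 has a PK column, and SAP 2.5.4 says "All available values obtained between two visits including unscheduled measurements will be assigned to the appropriate visit window". With several values in a window, "the scheduled measurement that is closest to the target date will be used". An unscheduled value is used only if the window has no scheduled one. EOT (Visit 49) is remapped to a nominal visit for efficacy only.
- **Follow-up sample.** Below Table 6, the 6-week post-treatment "measurement will be defined based on the sample collected at the follow-up Visit 50".
- **When blood is drawn.** Routine on-treatment PK samples are taken before dosing (Protocol 12.1.4, 12.1.8, 12.1.9, 12.1.11). The EOT sample (Protocol 12.1.12) carries no such condition.
- **Interruptions.** Protocol 11.1 allows a gap of up to 59 days ("3 IMP doses can be missed"). No PK rule mentions samples taken in or after such a gap.

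**The concern.** A trough is defined by time since the last dose. Table 6 carries no information on that: a window spans 6 to 12 dosing intervals, so a sample can sit near its target day and still come from a patient who stopped the drug weeks earlier. Three kinds of sample can enter a visit row without being troughs:

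1. the EOT sample of an early discontinuer, when it is the only scheduled value in its window;
2. a scheduled sample drawn while dosing is held, or soon after it restarts;
3. an SAE sample, when the window has no scheduled value.

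At stake are the long-term concentration profile by dose and the comparison by ADA status. If stopping or interruption differs between ADA groups, or builds up at certain visits, the tables could suggest an ADA effect on exposure or a drift over time that is really a mix of sampling times. Values below the quantification limit are set to half that limit (SAP 2.4.6), so very low off-drug values stay in the geometric mean.

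**Working it through.** The plan gives no figure of its own to reproduce. The check covers the windows, how often an EOT sample is selected, and the size of the effect.

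**1. Windows (Table 6, PK column).** All 27 window starts are consistent. The first is day 2, and each later one is the midpoint between neighbouring target days, e.g. Weeks 144 and 168: (1009 + 1177)/2 = 1093. Widths are 55 days (Week 4), 70 (Week 12), 84 (Weeks 24 to 84), 126 (Week 96), then 168 from Week 120 (126 at Week 504). In 14-day intervals, 84/14 = 6 and 168/14 = 12.

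**2. When an early EOT sample is used.** Take a patient seen on target at Week 144 (day 1009) who stops before Week 168 (day 1177). Week 156 is a dispensing visit without PK.
- EOT on days 1010 to 1092 falls in the Week 144 window. The day-1009 sample is closer to target, so EOT is not used.
- EOT on days 1093 to 1177 falls in the Week 168 window and is the only scheduled value, so it is used.

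With EOT uniform over the 168-day cycle (assumption), the share used is 85/168, about 50%. This treats Visit 50 as reserved for follow-up. It is the share of post-Week-96 discontinuations that contribute an EOT value, not the share that is far off trough. That depends on the gap from the last dose, which the documents do not give.

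**3. Size of the distortion.** The 60-day follow-up is meant "to capture the events observed within an approximately 5 half-lives of the last IMP" (SAP 2.1.3), so the half-life is h = 60/5 = 12 days. I also show h = 8 to 21 days as an assumed range. The documents give no PK model; first-order decay without absorption is assumed.

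- Level relative to a day-14 trough, d days after the last dose: R = 2^(−(d−14)/h).
- Geometric mean when a share p of values is at level R and the rest are true troughs: factor R^p.
- Arithmetic mean: factor (1−p) + pR.

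| Days since last dose | R, h = 12 (h = 8 to 21) | Fall in geometric mean, p = 5% (h = 8 to 21) | Fall in arithmetic mean, p = 5%, h = 12 |
|---|---|---|---|
| 20 | 2^(−6/12) = 71% (59 to 82%) | 1.7% (2.6 to 1.0%) | 1.5% |
| 28 | 2^(−14/12) = 45% (30 to 63%) | 4.0% (5.9 to 2.3%) | 2.8% |
| 59 | 2^(−45/12) = 7% (2 to 23%) | 12.2% (17.7 to 7.2%) | 4.6% |

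Day 59 is the longest permitted gap: 4 × 14 + 3 = 59, i.e. three missed doses plus the 3-day allowance.

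**4. Other directions.** An SAE sample at day 3 is 2^(11/12) = 189% of trough (144 to 259%), so it errs high. After a 59-day gap and restart at the same dose, let r = 2^(−14/12) = 0.445. The steady-state trough is r/(1−r) = 0.803 dose units, and 0.803 × 0.074 = 0.060 remains at restart. The first trough is then (1 + 0.060) × 0.445 = 0.472, and 0.472/0.803 = 59% of steady state (51 to 71%). Correct timing alone therefore does not make a just-restarted patient representative.

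**The case against.** Much limits the problem.

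- **Routine samples are mostly sound.** They are drawn before dosing on a 14-day schedule with ±3 days allowed (Protocol 8.1). This stands, though the visit injection is given only if 14±3 days have passed since the last one, so the protocol foresees visits off the dosing cycle.
- **Completers.** A per-protocol completer's EOT visit replaces Week 264 or is a planned later visit (Protocol 12.1), so the sample can be a true trough. Only early discontinuers are at issue.
- **Follow-up samples.** A reader might infer that Visit 50 samples also land in the on-treatment windows. The documents do not support this: Table 6 ends at Visit 49, and the text below it defines the follow-up value by Visit 50, most naturally as its own category. The SAP does not say outright that the sample is barred from the windows; one sentence would settle that.
- **SAE samples.** A reader might infer that they are routinely counted as troughs. Scheduled values take precedence, so they enter only when a window has none.
- **Reduced dose.** A reader might infer that 150 mg q2w is hit hardest, because interruptions for neutrophils, platelets or ALT precede it. This is not shown. The reduced dose is then kept for the rest of treatment (Protocol 11.1), so the triggering interruption comes once, before it starts, and samples drawn in that gap follow the earlier dose if dose is taken from the last injection.
- **Week 0.** SAP 2.4.6 already notes that EFC10832 placebo and SFY13370 tocilizumab patients have no Week 0 PK values.
- **Sub-study comparison.** Appendix K requires a stable, uninterrupted dose for 24 weeks, but for a within-patient Day 85 to Day 1 ratio after a device change. It shows that the dates can be used; it does not oblige the main study to adopt the same rule.
- **Robust summary.** The SAP also reports the median. With 5% low values it would sit at about the (0.50 − 0.05)/0.95 = 47th percentile of the true troughs, a small shift.

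What remains is that no rule keeps off-drug EOT and interruption samples out of the visit rows.

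**Conclusion.** The gap is real and modest. Followed as written, the main-study visit summaries and the ADA-and-PK tables can report as troughs some samples taken well beyond a dosing interval. EOT and interruption samples mostly bias the tables low; SAE samples can bias them high, so a uniform downward bias does not follow. On a 12-day half-life and an assumed 5% share, the geometric mean falls about 2% for a 20-day gap, 4% for 28 days and 12% at the 59-day limit. The first two are small, and the last would matter to a reader looking for a trend or an ADA effect. The size rests on first-order decay, the implied half-life and the assumed share, and the 50% selection figure rests on uniform EOT timing. PK is descriptive here and is neither a primary nor a listed secondary endpoint, so the safety conclusions are untouched. It should be corrected before the final analysis, but it is not a critical flaw.

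**What to change.** Add a sample-level rule to SAP 2.4.6 and refer to it from the ADA-and-PK part of SAP 2.4.8:

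1. Use only pre-dose samples taken within the planned dosing interval ±3 days of the last injection (11 to 17 days for q2w; state the matching range for the early weekly regimen). At h = 12 days, values in that range run from 119% to 84% of a day-14 trough.
2. Assign the dose group by the last injection before the sample.
3. Report off-schedule EOT samples and SAE samples separately, by days since last dose.
4. State that Visit 50 samples are used only for the follow-up category.
5. Flag samples soon after an interruption or dose change, or show the tables with and without them. Dropping every patient with a recent missed dose would describe only the fully adherent, which is a different quantity.
6. Give the number of samples excluded at each visit.

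The cost is SAP wording and programming. Last-administration dates are on the dosing CRF page (SAP 2.5.3) and collection dates are recorded (Protocol 9.3.1), so no new data are needed. The downside is slightly fewer values per visit.
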